Specific Aim 1: Assess the safety and feasibility of a new holding protocol for stable infants undergoing therapeutic hypothermia in the NICU. We hypothesize that there will not be a significant change in temperature variation, and there will be no increase in adverse events during holding.

Specific Aim 2: Assess mothers' and nurses' qualitative experience related to the holding during hypothermia intervention using a questionnaire with a combination of closed and open-ended questions. We hypothesize that mothers and nurses will respond positively to the opportunity to hold during hypothermia.

Adverse Effects: Given the vulnerability of infants in the NICU, potential adverse effects of the holding intervention and the monitoring strategy for these adverse effects are outlined here.

1. Holding during hypothermia could result in unintentional rewarming of the infant due to the proximity of the normothermic mother. In order to prevent rewarming, a thermal barrier will be placed between the mother and infant and the infant's esophageal temperature will be monitored every two minutes during holding and the intervention stopped early if the infant rewarms more than 1°C. Retrospective review of 16 medical records of infants treated with hypothermia at Maine Medical Center with gestational ages ranging from 34 -40+ weeks document a usual range of temperatures during cooling from 33-34°C (goal is 33.5°C)¹⁰. The research team has made the determination that the intervention will be stopped early if the infant rewarms more than 1°C based on this data.

2. Holding during hypothermia could result in dislodging of central lines. Only experienced NICU nurses will move the infant from the isolette into the mother's arms with assistance from a member of the research team. Critically ill infants that are intubated are considered too great a risk for accidental extubation and are therefore excluded.

C. Materials and Methods

Study Design: This is a single center safety study of the feasibility of a novel holding protocol for infants undergoing therapeutic hypothermia.

Study Population: As this is a pilot study to investigate concept and feasibility, a convenience sample of ten infants and their mothers in the MMC NICU being treated with TH will be recruited for the study according to the following criteria:

Inclusion criteria:

- Infant with gestational age ≥ 35 weeks treated with therapeutic hypothermia
- Infant **without** seizures in the first 24 hours on EEG

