- Infants who are clinically stable on bubble CPAP, nasal cannula or who have no respiratory support. This criterion MUST be confirmed by the Attending Neonatologist.
- Infants with all types of vascular access are eligible.
 - Use appropriate caution and attention to peripheral arterial lines and central lines (PICC, UAC, UVC, tunneled central catheters)
- Informed consent for research study signed by mother who is at MMC.

Exclusion criteria:

- Intubated status
- Use of inhaled nitric oxide
- Persistent pulmonary hypertension of the newborn
- Presence of seizures on EEG
- Use of vasopressors or paralytic agents
- Presence of chest tubes, wound vacuum or drains
- Neonatal abstinence syndrome

Eligibility for enrollment and consent process: [name] is the Neonatal Neurologist involved in the clinical care of all infants at MMC treated with therapeutic hypothermia. [name] will describe the research study to parents of infants who meet the inclusion criteria. [name] and/or the co-investigators will obtain signed informed consent from the mother on behalf of herself and from the mother or father on behalf of the infant.

Intervention: After obtaining consent, on the second or third day of hypothermia treatment, consented mothers will be assisted with holding their infants for a single 30-minute period. Holding will take place with the assistance of the NICU nurse according to the protocol developed for this study (see attached). The infant's vital signs will be measured before, during and after holding. Esophageal temperatures will also be measured and recorded every 2 minutes during holding to ensure that holding does not impact the infant's body temperature. If temperature deviations $+\text{-}1^{\circ}\text{C}$ occur or if the infant becomes hypoxic with oxygen saturations below 90%, the holding session will be terminated and the baby will be returned to his or her isolette. Prior observation of therapeutic hypothermia indicates that 1 degree Celsius is the average temperature deviation that occurs in typical therapeutic hypothermia sessions.¹⁰

Implementation of questionnaires:

- Parent Questionnaire:
A questionnaire using the Likert scale will be administered on paper to mothers 30-60 minutes after completion of the holding session. Results will be linked by a patient identification number to the hormonal samples. Responses to the questionnaire will be entered into a password-protected REDCap database.
- Nurse Questionnaire:

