The nurse questionnaire starts with an alteration of consent and consists of a combination of closed and open-ended questions that will be provided to the nurse on paper at completion of the holding procedure. The nurse's questionnaire will be identified by the case number that is assigned to the mother-infant dyad to protect their identities. The results of the questionnaire will be entered into a password-protected REDCap database.

Data collected:

As all of the patients treated with therapeutic hypothermia in our NICU are recorded in the Maine Medical Center Neonatal Encephalopathy REDCap database (IRB NET976245-1), we will use the same data for this holding study. In addition to the data already recorded in the REDCap database, we will also record the infant's current medication doses during holding, temperature recording taken at 2 minute intervals during holding and their vital signs before, during, and after holding. These vital sign recordings include temperature, heart rate, blood pressure, oxygen saturation and respiratory rate. If the infant does not have an arterial line in place, blood pressure will be measured every 10 minutes using a blood pressure cuff so as not to agitate the infant.

D. Analytical Methods

- Safety
Frequency of adverse events (as defined above) will be compared in this experimental cohort to data from historical controls in our therapeutic hypothermia database.
- Questionnaires
Answers from questions using a Likert scale will be simplified into nominal agree/disagree categories and compared with χ^2 test or Fisher's Exact Test as applicable. Open-ended responses will be analyzed by Thompson's general inductive technique.

E. References

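### Aim 1's temperature hypothesis has no planned analysis, and its adverse-event hypothesis rests on an undefined historical comparison that may not isolate the hold

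*Combined protocol and SAP*

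**What the plan says.** Specific Aim 1 (section B) states two hypotheses: that "there will not be a significant change in temperature variation", and that "there will be no increase in adverse events during holding". Both are about the hold itself.

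The Adverse Effects list in section B names two potential harms. One is unintended rewarming; the other is given as "Holding during hypothermia could result in dislodging of central lines".

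Section C plans a convenience sample of ten infants, each held once for 30 minutes on the second or third day of cooling. Eligible infants are at least 35 weeks and clinically stable on limited or no respiratory support; of that stability requirement the protocol says "This criterion MUST be confirmed by the Attending Neonatologist". Exclusions include intubation, inhaled nitric oxide, EEG seizures and "Use of vasopressors or paralytic agents".

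Under Data collected, the study draws on a database of every infant cooled in the unit. It adds temperatures every 2 minutes during the hold, and vital signs (temperature among them) before, during and after it.

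Section D then has one sentence on safety: "Frequency of adverse events (as defined above) will be compared in this experimental cohort to data from historical controls in our therapeutic hypothermia database".

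**The concern.** The analysis does not line up with the hypotheses, in three ways.

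- **Temperature variation.** This is the first half of Aim 1, and section D has no analysis of it. The 2-minute series and the surrounding vital signs are collected but not assigned to any summary or comparison.
- **Adverse events during holding.** This half is tied to the historical comparison. The plan does not say which database infants serve as controls, over what part of their cooling course events are counted, or whether the unit is the infant, the session or the hour. It is equally silent on whether events in held infants are counted over the hold or over the whole course.
- **Comparability.** The held infants are a selected group and no matching restriction on controls is stated. The 2-minute temperatures are recorded in addition to the database fields, so whether controls have comparable readings is an open question.

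The protocol calls itself a safety study, and Aim 1 is its safety claim. With the comparator open, a report of no increase could not be interpreted, and the choices that decide the result could be made after the data are seen.

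**Working it through.** The plan gives no derived figure to reproduce: there is no event rate, margin, significance level, power or number of controls. The check uses only the stated durations and sample size.

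**Inputs.** Cooling course 72 h (section A). Hold 30 min = 0.5 h, on day 2 or 3 (section C, Intervention). Ten infants (section C, Study Population). Temperature interval 2 min (section C, Data collected).

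**1. Held experience.** 10 × 0.5 h = 5 infant-hours if every hold runs its full length, and less if sessions stop early.

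**2. Three counting rules that the section D sentence allows.**

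- *Held infants over the hold, controls over the course.* 72 / 0.5 = 144. Equal event counts per infant would then mean an hourly rate 144 times higher during holding. Limiting controls to cooling days 2–3 still leaves 48 / 0.5 = 96, so restricting the days is not enough without a common time denominator.
- *Both groups over the whole course.* The hold is 1 window of 144, or 0.5 / 72 = 0.7% of the time. Assume for illustration a constant background rate and a hold that multiplies it by m. The whole-course rate then changes by (143 + m) / 144. With m = 10 this is 153 / 144 = 1.06, so a tenfold rise during the hold appears as about 6% over the course.
- *Both groups over a matched 30-minute window.* The ratio is 1, and the comparison does address the hold.

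The sentence does not choose among these.

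**3. Eligibility.** Database: all infants cooled in the unit. Held cohort: at least 35 weeks, stable, and free of the listed exclusions. The 16-record review cited under Adverse Effects covers infants "with gestational ages ranging from 34 -40+ weeks". It is not named as the control group, but it shows that some infants cooled at this centre fell below the study's gestational-age limit.

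**4. What ten sessions can support.** Exact (Clopper–Pearson) 95% intervals for the per-session risk:

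| Sessions with an event | 95% interval |
|---|---|
| 0/10 | 0 to 30.8% (upper limit 1 − 0.025^(1/10) = 0.308) |
| 1/10 | 0.3% to 44.5% |
| 3/10 | 6.7% to 65.2% |

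Even with no events, the data remain compatible with a risk of almost one in three. That supports an estimate, not a finding of no increase.

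**5. Event definition.** Section D refers back to adverse events as already defined. Adverse Effects lists rewarming of more than 1°C and line dislodgement. Intervention ends the session for deviations of 1°C in either direction or for saturation below 90%. These passages differ on what a temperature event is, and on whether low saturation is an event or only a reason to stop.

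**The case against.** The strongest reply is that an unspecified comparator is not a wrong one. The protocol says that all cooled infants are recorded in the database; it does not say that all will be controls, or that controls will be counted over 72 hours. Restricted controls in a matched window would comply with the present sentence. This stands. A reader might infer that the comparison cannot answer Aim 1 at all, or that a 144-fold mismatch is built in. The documents support neither: the mismatch belongs to one of several permitted readings.

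A reader might also infer that sicker controls would push the result towards no increase. Nothing in the documents shows that infants who are intubated or on vasopressors have more rewarming or line dislodgement, so that direction is not established. Closer temperature recording during the hold could push the other way.

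Finally, the protocol says "As this is a pilot study to investigate concept and feasibility", so a small sample and the absence of a power calculation are no fault here, and low power is not part of this point. Pilot status does not, however, supply the missing temperature analysis or define the comparator for a stated hypothesis of no increase. Bedside monitoring and session termination protect the infants but do not settle either matter.

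**Conclusion.** The point holds as a gap between aim and analysis, and should be fixed. Two parts rest on the text alone: section D contains no analysis of temperature variation or of the vital signs around the hold, and its historical comparison lacks control eligibility, window and unit.

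The size of any distortion depends on choices not yet recorded. It ranges from none (matched windows), through dilution of a hold effect (whole course in both groups), to a 144-fold difference in observation time (whole-course controls against a full-length hold). The 144 depends only on the stated durations but is conditional on that last reading. The 6% dilution figure further assumes a constant background rate and a tenfold rise. The net direction of bias is unknown.

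This is more than missing detail. Followed exactly, the plan would leave unused the data that bear most directly on Aim 1.

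**What to change.** Amend section D as follows.

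1. **Main safety analysis.** Describe temperature and vital signs within each infant before, during and after the hold, using the measurements already planned. Name the temperature summaries in advance, such as change in mean level and largest deviation from the pre-hold value. Where the monitor allows, chart pre-hold temperatures every 2 minutes too; 30 minutes would add 30 / 2 = 15 readings per infant. Without them, do not compare ranges across periods, because a range widens with the number of readings. The analysis should not depend on these extra readings.
2. **Events.** Report counts per session by event type with exact 95% intervals, as estimation and not as a test of no increase. Define the session to include transfer in and out, so that line dislodgement is captured, and state how many infants had a central line. Report actual hold duration and include sessions stopped early.
3. **Historical controls.** Keep them as descriptive context only. As far as the database allows, restrict them to infants meeting the same recorded criteria, on cooling days 2–3, with a common time denominator (one 30-minute window, or events per infant-hour).
4. **Definitions.** Reconcile the rewarming wording under Adverse Effects with the deviation wording under Intervention, and state whether low saturation counts as an event, before any events are counted.

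The cost is a few sentences and possibly the extra readings. The drawbacks are wide intervals, fewer eligible controls, and a pre-hold period that may look unusually quiet because holding starts when the infant is stable. Attending-confirmed stability and the timing of events may not be recoverable for historical infants.

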The Effects of Holding on Stress and Bonding in Mother-Infant Dyads During Therapeutic Hypothermia

Principal Investigator and Mentor: [name]
Co-Investigators: [name], MS4, [name], MS4

A. Introduction

Therapeutic hypothermia (TH) is a standard of care intervention that decreases death and disability in newborn term infants at risk for hypoxic brain injury. It involves placing the newborn infant on a cooling blanket for 72 hours in the Neonatal Intensive Care Unit (NICU). While TH has unmistakable neurological benefits to the newborn, prior research conducted with nurses and parents of infants treated with TH indicates that the experience is psychologically traumatic.¹⁻³ Specifically, both groups identified parents' inability to touch and hold their infants during TH as a major source of stress.

Past research demonstrates that the experience of being a patient in the NICU is associated with neonatal stress.⁴⁻⁶ Longitudinal studies show lasting effects of NICU-associated stress on infants as measured by persistent alterations in cortisol reactivity at eight months of age.⁷ It is likely that this stress profile also applies to infants who undergo TH while in the NICU. However, the association between TH and infant stress has not been studied quantitatively.

A complementary field of study has examined maternal holding as a therapeutic intervention for maternal and neonatal stress. Kangaroo, or skin-to-skin care, is widely used to facilitate mother-infant bonding and has been shown to have an analgesic effect on infants⁸ and cortisol lowering effects⁹ on mothers and infants. Likewise, oxytocin, a hormone produced by the pituitary gland and associated with maternal-infant bonding and stress reduction, has been shown to increase in mothers while they hold their infants¹⁴. It is unclear whether holding has the same effects during TH because skin-to-skin contact is not possible and morphine is often used to suppress infants' discomfort and shivering. The first specific aim of the present study is to evaluate the safety of allowing mothers to hold their infants during the TH protocol. The second specific aim is to investigate whether holding impacts mothers' and nurses' perception of stress during TH treatment.

[figure not shown]
B. Specific Aims and Significance

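### The χ²/Fisher analysis of the closed questions names no comparator or reference, and a two-group test would not address the Aim 2 hypothesis; report the proportion agreeing, with an exact interval, in each respondent group

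*Combined protocol and SAP*

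**What the plan says.** **Hypothesis.** Section B, Specific Aim 2: "We hypothesize that mothers and nurses will respond positively to the opportunity to hold during hypothermia".

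**Planned test.** Section D, Questionnaires: "Answers from questions using a Likert scale will be simplified into nominal agree/disagree categories and compared with" a χ² test or Fisher's exact test, whichever is applicable. The sentence names no second group, second time point or reference value. No significance level is given.

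**Comparator elsewhere in Section D.** The Safety entry does name one. The frequency of adverse events "will be compared in this experimental cohort to data from historical controls in our therapeutic hypothermia database". Nothing extends this to questionnaire answers or says that the database holds any.

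**Design.** Section C plans "a convenience sample of ten infants and their mothers in the MMC NICU". Every consented mother is to hold once. For mothers, "A questionnaire using the Likert scale will be administered on paper to mothers 30-60 minutes after completion of the holding session". The nurse form "consists of a combination of closed and open-ended questions that will be provided to the nurse on paper" when the hold ends. No survey before the hold and no non-holding group is described.

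**The concern.** The hypothesis is about a level: is agreement high among mothers, and is it high among nurses? Fisher's exact test, and χ² used on a two-way table, are about a difference. The documents do not say which difference is meant, and the design described supplies no control group and no baseline that would make it obvious.

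Two things follow. First, a two-group result would be silent on whether responses were positive, so the closed-question part of Aim 2 could be reported with a p-value that does not bear on its hypothesis. Second, because the contrast is left open, it could be chosen after the answers are seen.

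The stake is limited. The safety aim and the analysis of open-ended answers, which has its own named method, are untouched.

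**Working it through.** The plan gives no power, significance level or precision figure for the questionnaires, so there is nothing of its own to reproduce.

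**Inputs.** Ten dyads (Section C, Study Population). Assumptions: one mother form and one nurse form per dyad, so n=10 per group; independent respondents within a group; two-sided 5% level.

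**1. Does a mothers v nurses test follow the hypothesis?** This contrast is used only as the natural two-group example; the plan does not state it. Fisher's two-sided p adds the hypergeometric probabilities of all tables, with the same margins, that are no more likely than the one observed.

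| Mothers agree | Nurses agree | Fisher p | Bearing on Aim 2 |
|---|---|---|---|
| 10/10 | 10/10 | 1.0 | supports |
| 3/10 | 3/10 | 1.0 | contradicts |
| 10/10 | 5/10 | 0.033 | mothers positive, nurses split |
| 5/10 | 0/10 | 0.033 | mothers split, nurses negative |

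At 3/10 v 3/10 the observed table is the most likely one, so every table counts and p=1. At 10/10 v 5/10 all five disagreements fall in one group, with probability C(10,5)/C(20,5) = 252/15504 = 0.01625; doubling for the mirror table gives 0.0325. The last row is the same calculation with agree and disagree exchanged. Equal p-values thus go with opposite, or very different, answers to the hypothesis.

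**2. Could a one-sample χ² do it?** Take an even split as reference (an assumption; the plan gives none). Expected counts are 5 and 5, and χ² = (x−5)²/5 + ((10−x)−5)²/5 on 1 degree of freedom.

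- 10/10: 25/5 + 25/5 = 10.0, p=0.0016
- 9/10: 16/5 + 16/5 = 6.4, p=0.011
- 8/10: 9/5 + 9/5 = 3.6, p=0.058

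So a one-sample χ² would speak to the level of agreement. Fisher's test would not be available as its small-sample alternative, because it needs a two-way table.

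**3. What does direct estimation give?** The Clopper-Pearson 95% limits for x of n are the 0.025 quantile of Beta(x, n−x+1) and the 0.975 quantile of Beta(x+1, n−x). For x=n the lower limit is 0.025^(1/n) and the upper limit is 1.

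| Agree | Exact 95% interval |
|---|---|
| 10/10 | 69.2-100% (0.025^0.1 = 0.692) |
| 9/10 | 55.5-99.7% |
| 8/10 | 44.4-97.5% |
| 3/10 | 6.7-65.2% |

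These intervals describe the level in each group, which is what Aim 2 asks. They are wide: those for 9/10 and 3/10 overlap.

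**The case against.** **The sentence may mean a one-sample test.** It can be read as setting the agree count against the disagree count, in which case χ² does address the hypothesis, as step 2 shows. This stands in part. A reader might infer that no test named in the plan can answer Aim 2; that is too strong. What remains is that no reference is stated and that the Fisher alternative does not fit this reading.

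**Mothers v nurses is the reviewer's contrast.** This is correct. A reader might infer that it is the plan's intended comparison or the only one possible. The documents support neither: holding may fall on the second or third day, and items could be set against each other. None of these is named, and none would test a level of agreement. Section A says that "prior research conducted with nurses and parents of infants treated with TH indicates that the experience is psychologically traumatic", so an outside survey might also be in mind. Section D does not name one, and it would test a difference from that group.

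**The forms are not available to read.** Neither questionnaire is reproduced in the text available for review, and nothing follows from that absence. The documents therefore do not show that the scale has a neutral point, that any nurse answers more than once, or that nurse forms lack a respondent code. Section C says only that the nurse's "questionnaire will be identified by the case number that is assigned to the mother-infant dyad". Points on neutral answers and repeat nurses can only be conditional.

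**It is a small pilot with no confirmatory claim.** This stands and sets the severity. It also favours estimates with intervals over an unspecified significance test.

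A reader might also bring in Section A, which words the second aim as an effect on perceived stress, unlike Section B. That is a separate inconsistency and adds no weight here.

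**Conclusion.** The concern holds in a limited form. The closed-question analysis names neither a comparator nor a reference proportion, and a two-group χ² or Fisher test would not address the hypothesis that each respondent group is positive. The size of the problem is shown by p=1.0 at both 10/10 v 10/10 and 3/10 v 3/10. This rests on an assumed ten forms per group and on a contrast chosen for illustration; it is a logical demonstration, not a measure of error in a stated analysis. A one-sample χ² could serve, but only with a reference that the plan does not give.

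Severity is low: the closed-question part of Aim 2, in a ten-dyad pilot. Per-group proportions with exact intervals answer the question as posed and need no comparator.

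**What to change.** In Section D, replace the χ²/Fisher comparison as the Aim 2 closed-question analysis. For each item, separately for mothers and nurses, report the response distribution and the proportion agreeing with an exact 95% interval. Section C names a Likert scale only for the parent form, so use whatever response format the nurse form has.

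Keep a χ² or Fisher test only as secondary, and only if its comparator is named in advance. Analyse any mother-nurse contrast on shared items as pairs by dyad.

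Two conditional additions:
- If the scale has a neutral point, fix its coding in advance.
- If any nurse completes more than one form, present the nurse results descriptively or use one form per nurse.

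**Cost.** Mainly wording. If the nurse forms do not already allow repeat respondents to be recognised, an anonymous code would be needed, which may require ethics review. The drawback is imprecision: at n=10, even 8/10 leaves an interval of 44.4-97.5%. If the team also wants a criterion for a positive response, it should state it in advance and know its demands. A lower limit above 50% (an assumed value) needs at least 9/10. The chance of reaching that is 10 × 0.8⁹ × 0.2 + 0.8¹⁰ = 0.38 if true agreement is 80%, and 10 × 0.9⁹ × 0.1 + 0.9¹⁰ = 0.74 if it is 90%.
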